### **2.5.2 recMAGE-A3 ASCI preclinical experience**

The immune response induced by injections of the recombinant recMAGE-A3 protein formulated in different Adjuvant systems was investigated in the mouse model. The recMAGE-A3 protein was found to be weakly immunogenic by itself. However, in the presence of an adjuvant immunostimulant a robust immune response was induced, including MAGE-A3 –specific antibodies and T-cells. Immunized mice were protected against a challenge with tumor cells expressing MAGE-A3.

Extensive preclinical toxicity testing has been performed with the Adjuvant Systems that are used with recMAGE-A3, and with the various immunostimulants included in these Adjuvant Systems in combination with other cancer antigens (HER2/neu, P501) without any results that would raise concern about their safety in humans. See investigator's brochure.

### **2.5.3 recMAGE-A3 ASCI clinical experience**

In the terminated studies so far, a total of 1605 patients have received recMAGE-A3 alone or together with four different Adjuvant Systems, in a total of at least 10546 doses (cut-off date: April, 2010) (33). The AS15 Adjuvant System appeared to have the strongest and most robust

immunological response and was considered as having the highest potential to lead to improved clinical effect. Out of these 1605 patients, 1295 patients have received a total of some 7966 doses of the recMAGE-A3 + AS15 ASCI. In addition to this, it can be estimated that at least some 220 patients have been randomized to and received at least one dose of the recMAGE-A3 + AS15 ASCI in the two ongoing large randomized Phase III studies (in patients with NSCLC and melanoma) comparing this recMAGE-A3 + AS15 ASCI with placebo, but more exact figures cannot be provided because the data from these studies are blinded.

Most of the adverse events observed in all studies were to be anticipated and consist of local and systemic reactions (i.e., injection site reactions and constitutional symptoms such as myalgia, arthralgia, and fatigue). Almost all such events have been of Grade 1 or 2. Grade 3 symptoms were mainly general (i.e., fatigue, myalgia, and rigors/chills), except for local reactions associated with redness, pain, or swelling at the injection site; the majority of these symptoms were expected effects from using the AS15 adjuvant. Systemic Grade 3 events were rarely considered to be related to study treatment.

There were a total of 511 Serious Adverse Events (SAEs) in all clinical studies described in the Investigators Brochure (33). Of this number, only 23 events (4,5%) in four clinical studies were assessed as being possibly related to ASCI or control (placebo) treatment:

- Study 1: One Grade 3 event (injection site reaction); and one ungraded event (COPD exacerbation);
- Study 2: five Grade 4 events (fatigue, idiopathic pulmonary fibrosis, neutropenia, nonobstructive cardiomyopathy, idiopathic thrombocytopenic purpura); five Grade 3 events (pain in extremity, stress cardiomyopathy, pneumonia, Bowen's disease, eczema); four Grade 2 events (pyrexia, influenza-like illness, headache, and one unspecified event); and three Grade 1 events (pyrexia, hypersensitivity, COPD);
- Study 3: one Grade 2 event (allergic reaction);
- Study 4: one Grade 3 event (erysipelas); and two Grade 2 events (pyrexia, wound infection).

Such events have remained isolated cases, and almost all SAEs (488/511, or 95,5%) in these clinical studies were assessed by investigators as being unrelated to ASCI or control (placebo) treatment (29,33).

Biological indicators of auto-immunity have been observed infrequently. Very rare local clinical reactions (i.e. one transient episode of uveitis and one episode of localized vitiligo) and Grade 1-2 autoimmune events (i.e. hepatitis) have been recorded in three clinical studies where the recMAGE-AA3 antigen has been combined with two different immunological Adjuvant systems (i.e. CpG 7909 and AS15).

The non-related reported autoimmunity events were unexpected, as immunization against the MAGE-A3 antigen is not expected to lead to autoimmune reactions in humans. Even though a reasonable possibility of a causal association between autoimmune hepatitis and the recMAGE-A3 + AS15 ASCI has not been established, such an association cannot be excluded.

A large clinical safety database is currently available with the recMAGE-A3 protein in different formulations. These data show that these treatments have a very satisfactory safety profile, as most of the adverse events observed in all studies were to be anticipated and consist of low grade local and systemic reaction (i.e., injection site reactions and constitutional symptoms such as myalgia and fatigue). Almost all serious adverse events (488/511, or 95,5%) in these studies were rated by the investigators as being unrelated to the study immunization (29,33).

## 2.6.1 Rationale

Currently, the standard treatment for localized muscle invasive bladder cancer is radical cystectomy.

- **Many patients with muscle invasive bladder cancer will relapse after cystectomy**

The 10-year disease-specific and overall survival of patients with organ confined (defined as < pT3a) is 72.9% and 49.1%, rapidly decreasing to 33.3% and 22.8% for non-organ confined disease (13). There is thus a clear medical need for an additional anti-tumoral treatment in this population.

- **There is not enough evidence in favour of the routine use of adjuvant chemotherapy**

From scientific evidence so far available, it is unclear whether immediate adjuvant chemotherapy or chemotherapy at the time of relapse is superior or if the two approaches are equivalent with respect to the end-point overall survival. There is no additional effective treatment for the patient

population at high risk of relapse receiving adjuvant chemotherapy and this represents a significant unmet medical need (51).

- **MAGE-A3 is a factor of poor prognosis**

The interest in recMAGE-A3 ASCI treatment is further reinforced by the possible link between MAGE-A3 expression and shorter survival (34)

- **MAGE-A3 is tumor-specific, recMAGE-A3 + AS15 ASCI highly tolerated and shows promising Phase II results**

Taking into account the tumor-specificity of MAGE-A3, the high tolerability of recMAGE-A3 + AS15 and the promising results from the Phase II clinical trials in melanoma and lungcancer, EAU RF proposes to initiate a randomized, placebo-controlled clinical Phase II trial with recombinant MAGE-A3 (recMAGE-A3) combined with the AS15 adjuvant in patients with muscle invasive bladder cancer with MAGE-A3 expression after cystectomy.

This trial will assess whether adjuvant treatment with recMAGE-A3 + AS 15 ASCI after cystectomy is safe and effective and improves outcome of MAGE-A3 positive patients after cystectomy.

### **2.6.2 Rationale Protocol Amendment 4.0**

GlaxoSmithKline Biologicals recently reported the negative outcome of the MAGE3-AS15-NSC-003 (ADJ) (109493 - EudraCT number: 2007-001283-73) MAGRIT study (A double-blind, randomized, placebo-controlled Phase III study to assess the efficacy of the recMAGE-A3 + AS15 Antigen-Specific Cancer Immunotherapeutic as adjuvant therapy in patients with resected MAGE-A3-positive Non-Small Cell Lung Cancer (53). The analysis of MAGRIT confirmed the absence of treatment effect in any of the primary, secondary, or exploratory analyses. All aspects of the MAGRIT study have been carefully assessed, and unfortunately these investigations failed to identify a root cause for the lack of efficacy of the MAGE-A3 Antigen-Specific Cancer Immunotherapeutic (ASCI) in NSCLC that could be corrected in ongoing studies, including the MAGNOLIA study.

Furthermore, a comprehensive review of the Phase III results, together with all other available clinical and laboratory data with various recombinant proteins tested in different diseases and settings now suggests that the anticancer activity of this technology may well be limited to a

subgroup of Stage III melanoma patients with a specific predictive gene signature (52). A few patients in early metastatic melanoma also appear to benefit from this type of treatment.

Consequently, GSK Biologicals has decided to stop further development of recMAGE-A3 + AS15 as a standalone treatment for cancer patients. This decision is not motivated by any safety concern as confirmed by all Independent Data Monitoring Committees (IDMCs) overlooking the ASCI trials.

This decision implies that MAGE-A3 +AS15 CI will not be available for future treatment of bladder cancer patients which warrants a substantial amendment (4.0) of the MAGNOLIA study.

As of 23 September 2014, the recruitment was put on hold (sites were still allowed until 3 February 2015 to randomize patients that signed the informed consent or were in the screening process). As of Protocol Amendment 4.0, the recruitment will be stopped and the study population will be unblinded.

For patients randomized to the placebo group, no further protocol visits will be performed except for the concluding visit and no further doses will be administered. As it cannot be excluded that one or more patients may benefit from this treatment on an individual basis, patients receiving active treatment (patients not on placebo, and patients that have not already completed or interrupted their MAGE-A3 ASCI treatment) will be offered the option to continue the administration of the study treatment until the last dose is administered or until recurrence, whichever comes first, or until the patient or the investigator decides to stop the study treatment. Therefore, the study will continue only with patients from the active treatment group who will decide to stay in the study. Treatment will not be possible anymore after 30 November 2016.

During the treatment period, safety monitoring will continue as initially foreseen during the treatment period. In the best interest of the patient, additional biological samples for protocol research purposes (evaluation of the immune response, translational research) will not be taken nor collected.

The primary and secondary objectives will not be assessed as planned. All clinical data collected in the study will be analysed descriptively. By default, for each biological sample already collected in the scope of this study and not tested yet, testing will only be done if a scientific rationale remains relevant despite the premature termination of the study. In that case, testing will be in compliance with the protocol and ICF signed by the patient. The immune response will not be evaluated anymore as the immune response to IP administration was confirmed in other ASCI trials, but did not show any correlation with the potential efficacy.

### **3. STUDY OBJECTIVES & END POINTS**

#### **3.1 Primary Objective**

The primary objective of this Phase II study is to evaluate the clinical efficacy in terms of Disease Free Survival of recMAGE-A3 + AS15 ASCI versus placebo in the overall population.

#### **3.2 Secondary Objectives**

Secondary objectives are:

- To evaluate overall survival in the overall study population, in the subpopulations with and without use of neo-adjuvant chemotherapy and in the subpopulations with and without use of adjuvant chemotherapy
- To evaluate Disease-free (DFS) in the subpopulations with and without use of neo-adjuvant chemotherapy and in the subpopulations with and without use of adjuvant chemotherapy
- To evaluate Disease-free specific survival (DFSS) in the overall study population, in the subpopulations with and without use of neo-adjuvant chemotherapy and in the subpopulations with and without use of adjuvant chemotherapy
- To evaluate Distant metastasis-free survival (DMFS) in the overall study population, in the subpopulations with and without use of neo-adjuvant chemotherapy and in the subpopulations with and without use of adjuvant chemotherapy
- To evaluate the safety of recMAGE-A3 + AS15 ASCI in the overall study population, in the subpopulations with and without use of neo-adjuvant chemotherapy and in the subpopulations with and without use of adjuvant chemotherapy
- .
- Translational research:
  - a) To identify a gene signature predictive to recMAGE-A3+AS15 ASCI in MIBC.
  - b) To evaluate on exploratory basis a possible correlation between gene expression profile of the primary tumor and clinical efficacy of recMAGE-A3 + AS15 ASCI compared to placebo in terms of:
    - Disease-free Survival (DFS)
    - Overall survival

c) To evaluate expression of genes in a previously identified gene signature and evaluate their correlation with clinical efficacy of recMAGE-A3 + AS15 ASCI compared to placebo in terms of:

- Disease-free Survival (DFS).
- Overall survival.
- Disease-free specific survival (DFSS)
- Distant metastasis-free survival (DMFS).

d) To characterize of the tumor microenvironment and lymphocyte infiltration in the primary tumor and its recurrence lesions

As of Protocol Amendment 4.0 primary and secondary objectives of the MAGNOLIA study will not be assessed as planned. All clinical and safety data collected in the study will be analysed descriptively. Additional biological samples for protocol research purposes (evaluation of the immune response, translational research) will not be taken nor collected. By default, for each biological sample already collected in the scope of this study and not tested yet, testing will only be done if a scientific rationale remains relevant despite the premature termination of the study. In that case, testing will be done in compliance with the protocol and ICF signed by the patient. The immune response will not be evaluated anymore as the immune response to IP administration was confirmed in other ASCI trials, but did not show any correlation with the potential efficacy. See for rationale Section 2.6.2.

### **3.3 Primary Endpoint**

Disease-free Survival (DFS):

- Defined as the time from randomization to either the date of first recurrence of the disease or the date of death (whatever the cause), whichever occurs first.
- Types of recurrence to be considered as an event include loco-regional and distant metastases.
- In addition, any death occurring without prior documentation of tumor recurrence will be considered as an event (and will not be censored in the statistical analysis) as this approach is less prone to introduce bias.

- If no event has occurred by the time of the analysis, then the time to event will be censored at the date of the last assessment of the patient in question.
- Any new primary cancer at another site, including transitional carcinoma of the upper urinary tract, will not be considered as recurrence and should be reported as a SAE.

As of Protocol Amendment 4.0, the primary endpoint will not be analysed as planned. All clinical data collected in the study will be analysed descriptively. See for rationale Section 2.6.2.

### **3.4 Secondary Endpoints**

Overall Survival.

- Defined as the interval from randomization to the date of death, irrespective of the cause of death; patients still alive will be censored at the date of the last assessment.

Disease-free specific survival (DFSS).

- Defined as the interval from randomization to the date of first recurrence of disease or date of death due to bladder carcinoma, whichever occurs first. Patients without recurrence or death are censored at the date of last assessment. Patients without recurrence who die from another cause are censored at the date of death.

Distant metastasis-free survival (DMFS).

- Defined as the interval from randomization to the date of first distant metastasis or date of death, whichever occurs first. Patients alive and without distant metastasis are censored at the date of last assessment.

Adverse events.

- Occurrence of adverse events, including potential immune-mediated diseases

Serious adverse events.

- Occurrence of serious adverse events

To evaluate the efficacy of the recMAGE-A3 + AS15 ASCI compared to placebo in terms of DFS separately in the population presenting the predictive gene signature, and in the population of patients who do not present this signature

To evaluate the efficacy of the recMAGE-A3 + AS15 ASCI compared to placebo in terms of overall survival in the overall study population, in the population of patients presenting the predictive gene signature and in the population of patients who do not present this signature;

To evaluate the safety in the overall study population;

To evaluate Gene expression profiles of the primary tumor by microarray.

As of Protocol Amendment 4.0, the secondary endpoints will not be analysed as planned. All clinical data collected in the study will be analysed descriptively. See for rationale Section 2.6.2.

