#### **4. DESIGN OF THE STUDY**

This is a multicentre, prospective, randomized, placebo-controlled, parallel group, double-blind, trial to compare the efficacy and safety of recMAGE-A3 + AS15 ASCI intramuscular injections with Placebo intramuscular injections.

The target was to enroll 273 patients to be randomly assigned to 2 treatment schedules in a 2:1 ratio, 2 patients randomized for recMAGE-A3 + AS15 ASCI versus 1 patient randomized for placebo, either directly after recovery from surgery, or after recovery from adjuvant chemotherapy. Ten European countries are participating with a total of 50 sites. Sites contributed 0-28 screened patients in the recruitment period of 40 months. Enrolment in this study was competitive.

As of 23 September 2014, the recruitment was put on hold (sites were still allowed until 3 February 2015 to randomize patients that signed the informed consent or were in the screening process).

[figure not shown]
As of Protocol Amendment 4.0, the recruitment will be stopped and the study will be unblinded (see for rationale Section 2.6.2).

For patients randomized to the placebo group, no further protocol visits will be performed except for the concluding visit and no further doses will be administered. The study will continue only with patients from the active treatment group who will decide to stay in the study. Patients receiving active treatment (patients not on placebo, and patients that have not already completed or interrupted their MAGE-A3 ASCI treatment) will be offered the option to continue the administration of the study treatment until the last dose is administered or until recurrence, whichever comes first, or until the patient or the investigator decides to stop the study treatment. The duration of the treatment period will not exceed 108 weeks for any patient, comprising the entire period of treatment administration and excluding the concluding visit (Visit 14), provided there are no postponements. The concluding visit will take place at least 30 days after the patient's

last dose of study product. Treatment will not be possible anymore after 30 November 2016. The 2,5-year active follow-up period planned in the initial study protocol has been cancelled. The total duration of the study will be 7 years. Data collection will be organised by Remote Data Entry on Electronic Case Report Forms (eCRF).

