Procedures should be performed on 1. the planned visit or 2. within 14 days prior to the planned visit. Procedures should be performed before injection, not after injection of the study treatment.

Please note that as of Protocol Amendment 4.0 the follow-up visits (and the study procedures during follow-up phase, listed in Table 6 of the initial study protocol) have been cancelled.

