#### Visit 14: Concluding visit

This visit will take place at least 30 days after V13, approximately 120 weeks after first administration (V1) with a permitted deviation of up to 14 days, or in case of recurrence or early withdrawal.

The following procedures will be performed:

- Recording of concomitant medication
- Recording of (serious) adverse events and potential Immune-Mediated Diseases
- Routine physical examination including WHO performance status assessment
- Cross-sectional imaging or Magnetic Resonance Imaging (CT scan or MRI of chest, abdomen and pelvis)
- Pregnancy test

A pregnancy test will be repeated every 3 months for females of childbearing potential and should be performed at any time during the study for all women of childbearing potential if the investigator or patient suspects that pregnancy has occurred while the subject was being treated on protocol therapy.

- Blood sampling for safety

Note that as of Protocol Amendment 4.0, Smoking status and blood sampling for immunological examination (optional, if patient specifically consents to this), as mentioned in the original protocol, will not be performed anymore.

As of Protocol Amendment 4.0 the follow-up visits have been cancelled.

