### **7.3.3 Recurrence or progression**

All types of recurrence will be included i.e. local, regional and distant metastasis as well as second primary tumor of the upper urinary tract. In addition, all deaths occurring without prior documentation of tumor recurrence will be considered as an event. Any new primary cancer will not be considered as recurrence and should be reported as SAE.

All recurrences must be documented by radiological evidence or biopsy, as determined by the investigator.

[figure not shown]
Suspicion of relapse based on physical examination findings or laboratory signs must be confirmed by radiological examination and/or biopsy.

Equivocal findings on standard radiological imaging should be confirmed by repeated examinations or cytology/histology or other imaging techniques.

In the event of unequivocal, objective recurrence (at scheduled or unscheduled visit), the investigator will determine and record the recurrence, withdraw the patient from the study treatment

and perform all procedures as defined for Visit 14 before administration of chemotherapy to treat the recurrence. The investigator must inform the Sponsor as soon as possible.

The algorithm below summarizes how the date of recurrence should be determined.

Cxr, Chest X-Ray.

[figure not shown]
\* Date of imaging if equivocal, date of unplanned visit if symptoms present without imaging evidence.

\*\* CxR, CT scan/MRI, Bone scan, Biopsy of suspect lesion, etc.

\*\*\* Date of initial imaging (Day X) if equivocal, date of additional examinations (Day Z) if patient initially symptomatic without objective recurrence

[figure not shown]
**Scenario A:** As soon as a planned CT scan /MRI shows objective recurrence, the patient will be considered to have had a recurrence on the day of this planned imaging (Day X).

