#### 9.2.1 Patient withdrawal from study product administration

A ‘withdrawal’ from the study product(s) refers to any patient who does not receive the complete treatment, i.e. when no further planned dose is administered from the date of withdrawal. A patient withdrawn from the study product(s) may not necessarily be withdrawn from the study as further study procedures or follow-up may be performed as planned in this study protocol.

The investigator will document in the eCRF whether the decision to discontinue further treatment was made by the patient or the investigator and which of the following possible reasons was responsible for withdrawal:

- (Serious) adverse event (including intercurrent illness, unacceptable toxicity),
- Disease progression/recurrence,
- Protocol violation (specify),
- Other, eg. the occurrence of a second tumor that needs therapy (specify).

In this case, the concluding visit will be performed as described in Section 7.3.2.

If the patient refuses or cannot undergo these study procedures, he/she will be considered as withdrawn from study (Section 9.2.2).

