## **10. STATISTICAL CONSIDERATIONS**

### **10.1 Sample Size Calculation**

The assumptions for the sample size calculations were the following.

- Primary endpoint on which sample size is based is disease free survival (see Section 3.3)
- Hazard ratio of expected disease free survival of recMAGE-A3 + AS 15 ASCI treated patients relative to placebo treated patients that will be significant at the end of study is 0,75.
- Median Disease-Free Survival in the placebo groups is 24 months
- Recruitment period is 4-5 years
- All patients will be observed for a maximum of 5 years from their first study administration and with a minimum of 6 months after treatment completion.
- Null hypothesis H0: "there are no differences in expected disease free survival between the placebo treated patients and recMAGE-A3 + AS 15 ASCI treated patients.
- Alternative hypothesis H1: "the recMAGE-A3 + AS 15 ASCI treated patients have a different disease free survival compared to the placebo treated patients.
- Anticipated drop out percentage is 15 %
- One-sided alpha for final analysis is 0,05
- Power to detect a  $HR = 0,75$  is 50 %. Power to detect a  $HR = 0,65$  is 80 %.
- Randomization: 2 recMAGE-A3 + AS 15 ASCI patients versus 1 Placebo patient.
- Interim analysis planned when 65% of the total number of events have occurred.
- Calculations were done using East 5.3.

Based on these assumptions and in order to reach 155 events\* (see section 10.2), we needed a total of 273 patients for randomization. A total of 182 patients were to be randomized for treatment with recMAGE-A3 + AS 15 ASCI and 91 patients were to be randomized for treatment with placebo. Total number of evaluable patients (15 % drop out percentage) would be 231.

The power to detect a  $HR = 0,75$  (from 24 to 32 months) was 50%. The study would have 65% power if the true  $HR = 0,7$  (from 24 to 34 months) and 80% power if the true  $HR = 0,65$  (from 24 to 37 months).

Due to the Protocol Amendment 4.0, not all analyses described in this section will be performed and no interim analysis will be done. Please see Section 2.6.2 for the rationale.

\* 147 events without interim analysis

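### Under the Section 3.4 censoring rule, a by-arm overall survival curve or hazard ratio would lean towards active after Amendment 4.0, if survival after relapse was recorded before unblinding (minor)

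*Combined protocol and SAP*

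**What the plan says.** Section 3.4 runs OS from randomization to death from any cause; "patients still alive will be censored at the date of the last assessment". The date is each patient's own, and no section names a calendar cut-off.

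Section 4 gives the position after Amendment 4.0. For placebo patients, "no further protocol visits will be performed except for the concluding visit and no further doses will be administered". Active patients who have neither completed nor interrupted treatment may carry on until the last dose, recurrence or a decision to stop, with no dosing after 30 November 2016. "The 2,5-year active follow-up period planned in the initial study protocol has been cancelled". The notes to Table 5 in Section 7.2 say that "the follow-up visits (and the study procedures during follow-up phase, listed in Table 6 of the initial study protocol) have been cancelled", and the Visit 14 text in Section 7.3.2 repeats it: "As of Protocol Amendment 4.0 the follow-up visits have been cancelled". Under Section 7.3.3 the investigator who finds a recurrence must stop study treatment "and perform all procedures as defined for Visit 14 before administration of chemotherapy to treat the recurrence".

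On the earlier design, Section 10.1 still states: "All patients will be observed for a maximum of 5 years from their first study administration". Section 9.2.1 adds: "A patient withdrawn from the study product(s) may not necessarily be withdrawn from the study". Section 8.4 provides an eCRF form for deaths from progressive disease.

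On analysis, Sections 3.2, 3.4 and 10.3 say the clinical data will be described rather than analysed as planned. Section 10.3 names Kaplan-Meier and log-rank for disease-free survival (DFS) and leaves other outcomes to methods suited to the type of variable.

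**The concern.** The censoring rule stayed in place when the follow-up it relied on was removed. Censoring at the last assessment does little harm when every patient is followed on the same schedule, before and after relapse. After Amendment 4.0 that is no longer so. In the placebo arm, observation ends for an administrative reason, whatever the patient's disease status. Among continuing active patients it ends at relapse, after which most bladder cancer deaths occur. Active patients who had already relapsed or stopped cannot continue, so the added active-arm time is almost all recurrence-free.

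This is informative censoring in one arm only. Any OS summary that uses time at risk would flatter active treatment. The crude percentage dead would move slightly the other way, because active patients are watched longer. A report showing both could contradict itself with no treatment effect at all.

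**Working it through.** **1. The plan's own figure.** The documents give no OS figure. Their DFS power can be reproduced. With d = 147 events (no interim), 2:1 allocation and one-sided alpha 0.05, power = Φ(√(d × 2/3 × 1/3) × |ln HR| − 1.645), and √(147 × 2/9) = 5.716.
- HR 0.75: 5.716 × 0.2877 − 1.645 ≈ 0.00, power 50.0%
- HR 0.70: 5.716 × 0.3567 − 1.645 = 0.39, power 65.3%
- HR 0.65: 5.716 × 0.4308 − 1.645 = 0.82, power 79.3%

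Section 10.1 states 50%, 65% and 80%. These agree and are not in dispute.

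**2. Who adds OS time after unblinding.**

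| Patient at unblinding | OS observation ends |
|---|---|
| Placebo, any status | Concluding visit, near unblinding |
| Active, relapsed, completed or stopped | Near unblinding |
| Active, recurrence-free, on treatment, continues | Relapse, week 112, or about 30 days after 30 November 2016 |

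**3. Null model.**
- From the documents: 2:1 allocation, 40 months of recruitment, median DFS 24 months (hazard ln 2/24 per month, used in both arms), week 112 and the November 2016 limit.
- Assumed: uniform entry; 15% of DFS events are deaths without recurrence; median survival after relapse 6, 12 or 18 months; unblinding 1, 4 or 8 months after 3 February 2015; 50, 80 or 100% of eligible active patients continue.

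This gives 27 scenarios of 400,000 patients each, with true OS HR 1.0.

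**4. Hand check in one setting.** Take 10% of DFS events as deaths without recurrence, a post-relapse median of 12 months, unblinding 6 months after accrual ends, and all eligible active patients continuing. The post-relapse hazard is twice the DFS hazard, so among patients who relapse first 24-month survival is 2 × 0.5 − 0.25 = 0.75. True 24-month OS in both arms is 0.10 × 0.5 + 0.90 × 0.75 = 72.5%. The simulated Kaplan-Meier values are 72.7% for placebo and 76.1% for active. The placebo curve is right and the active curve is about 3.6 points too high. The HR is 0.90 and the person-time rate ratio 0.91. Crude deaths are 30.8% active and 29.9% placebo. With nobody continuing, the HR is 1.00 and the curves read 72.6% and 72.7%.

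**5. Range over the scenarios.**

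| Situation | OS HR | 24-month difference, active minus placebo (points) |
|---|---|---|
| Rule as written | 0.82 to 0.97 | +1.2 to +7.3 |
| Survival after relapse recorded before unblinding in half of patients | 0.84 to 0.97 | +0.8 to +4.8 |
| Same, in none | 0.98 to 1.02 | −0.2 to +0.3 |
| Half of later deaths captured (80% continue) | 0.91 to 0.97 | not tabulated |
| All later deaths captured (80% continue) | 0.96 to 1.01 | not tabulated |
| Common cut at unblinding | 0.99 to 1.02 | −0.4 to +0.3 |

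As written, by unblinding at 1, 4 and 8 months, the HR is 0.82 to 0.92, 0.87 to 0.94 and 0.91 to 0.97. The mid case (4 months, 80%, 12 months) gives 0.90; unblinding at 12 months gives 0.95 to 0.98. The rate ratio is 0.83 to 0.98 and the 12-month difference −0.1 to +1.6 points. Crude deaths are 0.2 to 2.0 points higher on active, with mean observation of 19.2 to 25.9 months against 16.8 to 23.7 on placebo. Distant metastasis-free survival (DMFS) moves less: HR 0.95 to 0.99.

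**6. Size against noise.** With 83 patients (the count when recruitment was put on hold) and 80% continuing, about 2 to 5 active patients are censored at relapse. About 1 to 4 deaths go uncounted, against 18 to 35 counted. In the step 4 setting the SD of log HR is about 0.45 and the shift is −ln 0.897 = 0.109, so 0.109/0.45 = 0.24 of one SD. In small-trial runs at 80% continuation, the 24-month shift of about 2 to 7 points compares with an SD of 11 to 14 points. HR falls below 1 in 56 to 67% of null trials, against 48 to 51% with a common cut.

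**The case against.** The strongest reply is that nothing planned is affected. The analysis is descriptive, Section 10.3 names Kaplan-Meier for DFS only, and no section promises OS by arm. That stands, and it is the main reason the point is minor. It does not remove the point: all clinical data are still to be described, and Kaplan-Meier is a natural choice for a censored outcome.

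Second, the condition is unproven. Sections 10.1, 9.2.1 and 8.4 suggest that survival after relapse was recorded before unblinding, but the cancelled Table 6 is not available. Without that recording both arms are censored at relapse alike, and there is no lean. This also stands, as a condition on the conclusion.

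Third, Section 9.2.1 applies equally to active patients who relapse after unblinding. Section 9.1 still mentions phone contacts, Section 8.8 refers to later contacts, and the stated 7-year duration runs well beyond November 2016. Late deaths might therefore be captured. None of these passages schedules a survival contact, and Section 8.11 does not oblige investigators to look for late SAEs. Partial capture is possible, though, and would shrink the effect: half capture both before and after unblinding gives an HR of about 0.96 to 0.97 in mid-range cases.

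Fourth, 0.82 is a corner case. It needs unblinding within one month, full continuation and short survival after relapse together. That is fair; about 0.90 is the better single figure if survival after relapse was recorded before unblinding and later deaths are not captured.

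**Conclusion.** The concern holds as a minor, conditional point. If OS is shown by arm with a time-at-risk method, and survival after relapse was recorded before unblinding, the rule as written favours active with no true effect in every scenario tried. The size depends on the unblinding date, uptake of continued treatment, survival after relapse and late-death capture, none of which the documents give. It approaches zero if post-relapse survival was never recorded or all later deaths are found. Development of the product as a standalone treatment has stopped and no decision rests on OS, so the practical risk is a misleading figure in the final report or publication.

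**What to change.** Add to Sections 3.4 and 10.3 that any by-arm description of OS, and for consistency DMFS, uses one calendar cut-off for both arms: the unblinding date under Amendment 4.0, named in the analysis plan before analysis. Then:
- Count events up to the cut-off. Censor all other patients at the earlier of the cut-off and the date last known alive (for DMFS, last assessed free of metastasis). Censoring everyone at the cut-off itself would overstate 24-month OS by 2.0 to 3.3 points under an assumed 15% loss to follow-up by 24 months.
- If sites unblinded on different dates, use the earliest. With dates spread over 3 or 6 months, the earliest date gives a null HR of 0.99 to 1.01; the latest gives 0.96 to 0.99.
- Report follow-up by arm, say whether survival after relapse was recorded before unblinding, and list later active-arm events separately as single-arm data.

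This needs no new data. The comparison loses active-arm time after unblinding, which has no placebo counterpart, and a few months in both arms if site dates differ. A stated limitation beside any by-arm OS display would be a weaker alternative: it warns the reader but leaves the lean in place.
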